#### **9.1.10 Pregnancy**

In the event a subject becomes pregnant during the study, she should be withdrawn. However, the subject will be encouraged to complete the post-treatment follow-up portion of the study to the extent that study procedures do not interfere with the pregnancy.

In addition, any pregnancies in the partner of a male subject during the study or for 60 days after the last dose should also be recorded.

If the pregnancy occurs at any time during the study and the 60 days of last dose of active study medication, the pregnancy should be reported immediately to the Sponsor, using a pregnancy notification form.

Study subjects will give consent on enrollment that the Investigator will report any pregnancy during the study to the Sponsor and that they will be asked to provide information about her pregnancy, delivery, and the health of her infant until age one month. Payment for all aspects of obstetrical care, child, or related care will be the subject's responsibility.

All reported pregnancies will be followed up to final outcome, using the pregnancy and pregnancy follow-up forms. The outcome, including any premature termination, will be reported to the Sponsor. An evaluation after the birth of the child may also be conducted.

Pregnancy complications must be recorded as adverse event(s). If the infant has a congenital anomaly/birth defect this must be reported and followed up as a serious adverse event.

#### **9.1.11 ECG Procedure**

All ECG's throughout this study will be performed as standard triplicate 12-lead ECG's, except the ECG at Screening. ECG's will be recorded after 5 minutes in a supine position. Only the Triplicate ECG's will be recorded at least 1 minute apart from each other, not exceeding a time period of 5 minutes for the completion of all three ECG's.

The Investigator (or designee) will interpret the ECG's by use of an electronic measurement using the following categories: within normal limits, abnormal but not clinically significant, or abnormal with clinical significance. ECG's are performed according to the [Table 16-1](#). The following parameters will be recorded from the subject's ECG trace: heart rate, QT interval, PR interval, QRS interval, R-R interval, and QTcF (corrected) using the Fridericia correction ( $QTcF = QT \div \text{cube root of the R-R interval}$  [where R-R is the duration of the entire cardiac cycle]).

When ECGs are to be collected at the same time point as a blood collection, ECGs should be collected first to avoid any artificially increased heart rates due to the blood collection.

The mean value of the 3 baseline ECG measurements collected at Day -2 will serve as each subject's baseline for all post-dose comparisons. ECG measurements are to be collected during screening and on Day -2 and 77 before subjects are connected to the ABPM device. Additionally, ECG measurements are taken on Day 5 and Day 82, after ambulatory devices (Holter and ABPM) are removed.

In some cases, it may be appropriate to repeat abnormal ECGs. If a machine-read QTc value is prolonged, repeat measurements may not be necessary if the Investigator's interpretation determines that the QTc value is in the acceptable range.

### **9.1.12 Check-in Procedure**

All subjects will check in to the clinic in the morning for the In-house Periods 1 and 2. Eligibility will be confirmed, and the following will be assessed:

1. Positive alcohol breath test.
2. Positive urine drug screen.
3. Positive urine pregnancy test for WOCBP.
4. Any use of prescription or non-prescription medicine other than the allowed concomitant medications within the last 12 hours.
5. Any medical condition that could interfere with glucose metabolism, as judged by the Investigator.

Subjects who fulfill one or more of the stated criteria at check-in, will not be able to continue onto the treatment period. The treatment period will be rescheduled. Each treatment period may be rescheduled no more than twice. After that, the subject will be excluded from the study. Replacement of subjects for the dosing period may be permitted to enroll sufficient subjects into the study after discussion with Sponsor and Investigator.

### **9.1.13 Standardized Meals**

During in-house period, subjects will receive standardized meals. The standardized weight maintaining meals will be provided using estimated BMR  $\times$  activity factor of 1.5 to determine daily caloric intake.

### 9.1.14 ABPM

The 24-hour blood pressure will be measured by an ABPM device. A validated, reliable, automated, and accurate monitor will be used with a storage function. Blood pressure measurements will be started overnight on Day -2 to familiarize the subjects with the device. During this period, measurements will be taken every 2 hours until the morning of Day -1.

The baseline assessment period will start in the morning of Day -1 until Day 1. Measurements will be taken hourly up to 14 hours and then 2-hourly until 24 hours.

The post-dose assessment period will start in the morning of Day 1. Measurements will be taken hourly up to 14 hours and then 2-hourly until 24 hours every day (for every 24-hour period), until the morning of Day 5.

Additionally, subjects will be connected to the ABPM system again on Day 77. Blood pressure measurements will be started overnight on Day 77 to familiarize the subjects with the device. During this period, measurements will be taken every 2 hours until the morning of Day 78.

The post-dose assessment period will start in the morning of Day 78. Measurements will be taken hourly up to 14 hours and then 2-hourly until 24 hours every day (for every 24-hour period), until the morning of Day 82.

Time points stated in the [Table 16-1](#). Adequate cuff size will be documented for each subject, after determination of the patient's non-dominant arm circumference. Subject's bedtime and awakening will be recorded to divide the downloaded data into diurnal and nocturnal values. Depending on available PK and safety data, timepoints for measurements may be adjusted for the following cohorts.

Specifications about the ABPM model will be described in the Operations Manual and ABPM Procedure Manual, as well as detailed instructions of blood pressure frequency, data management and medical review.

### 9.1.15 Holter Monitoring

24-hour heart rate activity will be continuously recorded with an ambulatory Holter monitoring system (eg, Mortara surveyor). Holter electrodes (12 lead, 3-channel placement) will be placed to the subject's chest and will be attached to a small recording monitor. The Holter monitor will be carried in a pocket or small pouch. Subject's activities or exercises will be recorded while wearing the monitor.

Specifications about the Holter model will be described in the Operations Manual and Holter Procedure Manual, as well as detailed instructions of data management and medical review.

### 9.1.16 Pharmacokinetic Assessments and Schedule

Blood for PK analysis of the study drugs will be collected at the time points indicated in the [Table 16-1](#) Schedule of Events and follow the PK sampling schedule [Table 9-3](#). One 2-mL sample per scheduled time point will be collected to provide a minimum of 500 µL of serum for PK measurements and 500 µL of serum as a secondary back-up sample. Instructions for sample processing and shipment will be provided in the PK Sample and Shipping Instructions. Pre-dose sampling will be taken within 10 minutes before dosing. Dosing should occur at approximately 08:00 h on every dosing day. The actual time of PK sampling should not deviate from the nominal time by more than  $\pm$  5 minutes during the Inpatient Period, and by more than  $\pm$  2 days for the Elimination Period and Follow-up Visit. If Visit during elimination period or follow-up visits will be performed on a different day, the time point for the sampling will still be in the morning, preferably at the same time (at approximately 08:00h). The actual time of dosing, actual sampling dates and times should be recorded.

**Table 9-3 PK Sampling Schedule for cohorts 1-1 and 1-2**

| PK sampling schedule          |         |         |                                     |
|-------------------------------|---------|---------|-------------------------------------|
| Treatment Period              | Week 1  | Day 1   | Pre-dose 1 st dosing     |
|                               |         |         | 8 h after 1 st dosing    |
|                               | Day 2   |         | 24 h after 1 st dosing   |
|                               |         | Day 3   | 48 h after 1 st dosing   |
|                               | Day 4   |         | 72 h after 1 st dosing   |
|                               | Week 2  | Day 8   | Pre-dose 2 nd dosing     |
|                               |         | Day 10  | 48 h after 2 nd dosing   |
|                               | Week 3  | Day 15  | Pre-dose 3 rd dosing     |
|                               | Week 4  | Day 22  | Pre-dose 4 th dosing     |
|                               | Week 5  | Day 29  | Pre-dose 5 th dosing     |
|                               | Week 6  | Day 36  | Pre-dose 6 th dosing     |
|                               | Week 8  | Day 50  | Pre-dose 8 th dosing     |
|                               | Week 9  | Day 57  | Pre-dose 9 th dosing     |
|                               | Week 12 | Day 78  | Pre-dose 12 th dosing    |
|                               |         | Day 80  | 48 h after 12 th dosing  |
|                               |         | Day 81  | 72 h after 12 th dosing  |
| Elimination Period ( $\pm$ 2) | Week 13 | Day 85  | 168 h after 12 th dosing |
|                               | Week 15 | Day 99  | 504 h after 12 th dosing |
| F/U ( $\pm$ 2)                | Week 17 | Day 113 | 840 h after 12 th dosing |

**Table 9-4 PK Sampling Schedule starting from cohort 1-3**

| PK sampling schedule    |          |         |                                     |
|-------------------------|----------|---------|-------------------------------------|
| Treatment Period        | Week 1   | Day 1   | Pre-dose 1 st dosing     |
|                         |          |         | 8 h after 1 st dosing    |
|                         |          | Day 2   | 24 h after 1 st dosing   |
|                         |          | Day 3   | 48 h after 1 st dosing   |
|                         |          | Day 4   | 72 h after 1 st dosing   |
|                         |          | Day 5*  | 96 h after 1 st dosing   |
|                         | Week 2   | Day 8   | Pre-dose 2 nd dosing     |
|                         |          | Day 10  | 48 h after 2 nd dosing   |
|                         | Week 3   | Day 15  | Pre-dose 3 rd dosing     |
|                         | Week 4   | Day 22  | Pre-dose 4 th dosing     |
|                         | Week 5   | Day 29  | Pre-dose 5 th dosing     |
|                         | Week 6   | Day 36  | Pre-dose 6 th dosing     |
|                         | Week 8   | Day 50  | Pre-dose 8 th dosing     |
|                         | Week 9   | Day 57  | Pre-dose 9 th dosing     |
| Week 12                 | Day 78   |         | Pre-dose 12 th dosing    |
|                         |          |         | 8 h after 12 th dosing   |
|                         |          | Day 79  | 24 h after 12 th dosing  |
|                         |          | Day 80  | 48 h after 12 th dosing  |
|                         |          | Day 81  | 72 h after 12 th dosing  |
|                         | Day 82** |         | 96 h after 12 th dosing  |
| Elimination Period (±2) | Week 13  | Day 85  | 168 h after 12 th dosing |
|                         | Week 15  | Day 99  | 504 h after 12 th dosing |
| F/U (±2)                | Week 17  | Day 113 | 840 h after 12 th dosing |

\*Sampling on Day 5 will start with Cohort 1-4 and will not be taken for cohort 1-3.

\*\* Sampling on Day 82 will be optional for cohort 1-3 but will be taken in cohort 1-4.

Available PK data will be utilized for decision making in dose escalation meeting. Based on results, the PK sampling schedule may be adjusted. The total number of blood sampling events will not exceed the total number of blood sampling events originally planned.

### 9.1.17 Laboratory Pharmacodynamic Assessments

Blood for analyses of PD assessments will be collected at the time points indicated in the [Table 16-1](#) and [Table 16-2](#). Sampling for incretins/ metabolic hormones (GLP-1, GIP,

Version 5.0\_02Jul2019

Glucagon, FGF21, Leptin), serum lipid profiles and particles (total cholesterol, LDL-C, LDL-P (particles), HDL-C, HDL-P (particles), VLDL-C, VLDL-P (particles), Triglyceride, Free Fatty Acids), amino acid profile (taurine, aspartate, hydroxyproline, threonine, serine, asparagine, glutamate, glutamine, sarcosine, alpha-amino adipate, proline, glycine, alanine, citrulline, alpha-aminobutyrate, valine, cystine, methionine, homocitrulline, cystathionine, alloisoleucine, isoleucine, leucine, tyrosine, phenylalanine, argininosuccinate, beta-alanine, beta-amino isobutyrate, homocystine, gamma-aminobutyrate, tryptophan, hydroxylysine, ornithine, lysine, histidine, arginine), glucose metabolism parameter (FPG, Fasting insulin, fasting c-peptide, HbA1c), inflammatory marker (Adiponectin), ketone bodies (BHB) and bone metabolism parameters (CTX-1, OC, P1NP) will be collected.

Instructions for sample processing and shipment will be provided in the laboratory manual. All samples, including pre-dose sampling on Day 1 will be taken within 30 minutes before dosing.

#### **9.1.18 MRI/MRI-PDFF**

Magnetic resonance imaging-derived proton density fat fraction (MRI-PDFF) deems as a noninvasive, quantitative, and accurate measure of liver fat content/ hepatic steatosis grade in this study to identify the study population and assess the treatment response in subjects with NAFLD. For subjects in cohort 1-5 and up, the assessment of visceral fat will also be assessed via MRI imaging at Screening, during week 8 and week 12, together with the MRI-PDFF assessment.

MRI-PDFF will be performed using a standardized imaging acquisition calibration protocol and the results a will be determined by central reader at screening (as baseline value) and during week 8 (close to Day 57 as possible, but prior to dosing on Day 57), and week 12 (close to Day 85 as possible, but after ABPM and Holter are disconnected on Day 82; but prior to the PK sampling on Day 85).

For details please see the Operations Manual.

#### **9.1.19 VCTE**

One-dimensional vibration controlled transient elastography (VCTE) assessed via eg, FibroScan (EchoSensTM, Paris, France) will be used in this study.

At Screening, subjects will be examined with the FibroScan to assess the controlled attenuation parameter (CAP) in order to qualify for the inclusion in the study.

For subjects participating in cohort 1-4 and up, FibroScan assessments will be performed on Day 85 to assess a change from baseline in CAP and LSM.

It is a device, that uses non-invasive, one-dimensional vibration controlled transient elastography (VCTE). The device generates a low-frequency shear wave from a probe applied to the subject's skin between the ribs. The speed of the wave spread is then measured between two points within the liver to allow the livers stiffness to be

quantified. The wave will travel more rapidly through stiff tissue. An examination using the FibroScan consists of ten signal acquisitions at a single point; the whole process lasts around 15 minutes. The results are instantly displayed on a screen and the value for stiffness can be matched to a fibrosis stage.

For details please see the Operations Manual.

#### **9.1.20 Immunogenicity Assessments**

Blood samples will be acquired to determine ADAbs, nAbs and anti -PEG within 30 min prior to the first dosing on Day 1, post first dosing on Day 22, 50, 78, 85 and 99. Post first dose samples will be taken at the same time point of safety blood sampling or collection of other blood samples.

Instructions for sample processing and shipment will be provided in the PK/Immunogenicity Sample and Shipping Instructions.

#### **9.1.21 Tolerability Assessments**

After injection of the study drug, the injection site will be marked with an indelible marker/pen. Assessment of study drug injection site will be performed within 30 minutes of pre-dose, at 4 and 12-hour post-dose on Day 1 with a window of  $\pm$  30 minutes. Assessment of study drug injections on the other dosing days will be performed at least 30 minutes post-dose, and then daily during the in-house periods and at outpatient visits on non-dosing days in the morning, approximately at the time of the dosing on dosing days. Last injection site inspection will be performed on Day 85.

The local reaction from the injection site will be evaluated quantitatively using a Draize scale or similar scale. If an injection site reaction like pain on palpation, itching, erythema, edema, induration is observed, it must be recorded as an AE and then will be evaluated using the following scale:

Erythema will be evaluated as follows:

- 0 – No erythema
- 1 – Very slight erythema (barely perceptible)
- 2 – Well-defined erythema
- 3 – Moderate to severe erythema
- 4 – Severe erythema (beet redness) to slight eschar formations (injuries in depth)

Edema will be evaluated as follows:

- 0 – No edema
- 1 – Very slight edema (barely perceptible)
- 2 – Slight edema (edges of area well defined by definite raising)
- 3 – Moderate edema (raised approximately 1 mm)

- 4 – Severe edema (raised more than 1 mm and extending beyond the area of exposure)

For the irritation assessment, all irritation events will be documented as AEs. The diameter of the affected area will be measured with a paper measuring tape in centimeter (cm) and the condition of the injection site will be recorded. Digital photography will be used to document all positive injection site reactions. In case of clinically significant injection site reactions, subjects may undergo a dermatological consultation and/or cutaneous biopsies for further histological examination of the injection site reaction. Biopsies will be performed using a 4-mm punch biopsy centered on the injection site. The biopsy area will be anesthetized with lidocaine prior to the biopsy. Wound closure will be performed with Steristrips. If stitches are necessary to close the punch area, they will be removed approximately 2 weeks later. The time between injection and biopsy will be recorded. Microscopic and histological examination of the punch biopsies will be performed at a qualified lab.

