## 6.0 STUDY DESIGN AND DESCRIPTION

### 6.1 Study Design

This is a randomized, placebo-controlled, multiple-ascending dose study to investigate the safety, tolerability, PK and PD of SC administration of HM15211, conducted in 1 part.

[figure not shown]
This study will be single-blind and conducted in up to 6 cohorts comprising a total of up to 72 obese subjects with NAFLD. Each cohort will enroll subjects to ensure that at least 12 subjects per cohort will complete the study. Subjects will be randomized to investigational product (IP) or placebo in a 3:1 ratio via an Interactive Web Response System (IWRS). Per cohort (n=12 subjects), 9 subjects will be randomized to IP and 3 subjects to placebo. Cohorts may partially overlap after at least 9 subjects have completed 2-4 weeks of treatment (2 weeks of treatment is reached at Visit week 3) and a dose escalation decision has been made. Study drug will be administered weekly over a period of 12 weeks.

Based on available safety, tolerability, and PK data of each cohort, and following a safety review and dose escalation meeting between the investigator and the sponsor, dose escalation to the next cohort may proceed. Cohorts will start in sequential order but may overlap partially during execution. Replacement of dropouts and withdrawals may take place.

[figure not shown]
Each subject will undergo a screening visit, 2 in-house/ treatment periods and multiple outpatient visits. A final follow-up visit that will conclude subject study participation.

The duration of participation in this study including Screening, Treatment and Follow-up will be approximately 23 weeks for each subject including 12 weeks of treatment period.

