### In-house Period 1:

Day -2: Subjects will check in to the clinic in the morning of Day -2 for a 10-day in-house period. They will receive standardized meals throughout their in-house stay. A 12-lead standard ECG will be performed. Subjects will be connected to an ABPM system for measurement of blood pressure (BP), and measurements will be started overnight on Day -2 to familiarize the subjects with the device. Measurements will continue until the morning of Day 5.

Day -1: In the morning of Day -1, subjects will get connected to a Holter ECG for continued measurement of the heart rate activity until the morning of Day 5.

Only 24-hour monitoring data from Day -1 to Day 1 will be used for the monitoring evaluation as baseline assessments for ABPM and Holter ECG monitoring. For measuring timepoints, please see sections [9.1.14](#) and [9.1.15](#).

Subjects will be randomized to weekly SC injections of HM15211 or placebo. Randomization will take place as close to the drug administration as possible.

Day 1: On Day 1, after an  $\geq 10$  h overnight fast, subjects will be dosed with HM15211 or placebo at approximately 08:00 hours (t=0), through SC injection into the abdominal wall by qualified study staff. Measurements of vital signs, blood sampling for PK at pre-dose and 8 hours after dosing and sampling for laboratory parameters including incretins/metabolic hormones, lipid profiles and particles, amino acid panel, bone metabolism parameters, glucose metabolism parameters, ketone bodies, local injection site evaluation, and evaluations for safety parameters will be performed, at timepoints stated in [Table 16-1](#).

ABPM and Holter ECG monitoring will be continued until the morning of Day 5 for the post-dose evaluation.

Subjects will continue to stay in-house for safety evaluations, PK and PD assessments as stated in the SOE. They will be released from the CRU in the morning of Day 8, after the second dose of the weekly study drug is administered. They will return for multiple outpatient visits.

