#### Outpatient Visits:

Subjects will return to the CRU every week (Days 10, 15, 22, 29, 36, 43, 50, 57, 64, 71) in order to undergo assessments as described in [Table 16-1](#). Subjects will receive the injection of the study drug in an outpatient fashion to ensure compliance on Days 15, 22, 29, 36, 43, 50, 57, 64 and 71.

MRI/MRI-PDFF: Subjects will undergo an MRI-PDFF assessment during week 8, as close as possible to Day 57, but prior to the Day 57 (week 9) Dosing.

During all outpatient visits, blood samples for PK analysis, exploratory endpoints and safety assessments will be performed as stated in the [Table 16-1](#).

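### For doses 3 to 10 (8 of 12) the injection site must be inspected only on the day of injection, and nothing requires the earlier site to be looked at again

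*Protocol*

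**What the plan says.** Section 9.1.21 (Tolerability Assessments) has the site marked with an indelible pen after injection and sets three layers of inspection:

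- **Day 1:** shortly before dosing and then "at 4 and 12-hour post-dose on Day 1 with a window of" 30 minutes either way.
- **Other dosing days:** "Assessment of study drug injections on the other dosing days will be performed at least 30 minutes post-dose".
- **After the dosing day:** "and then daily during the in-house periods and at outpatient visits on non-dosing days in the morning". The last inspection is on Day 85.

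An observed reaction must be recorded as an adverse event and scored for erythema and edema. The diameter is measured and positive reactions are photographed.

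The visit plan is in sections 6.1 and 6.2. Dosing is fixed by "Study drug will be administered weekly over a period of 12 weeks". For the first in-house period, "They will be released from the CRU in the morning of Day 8, after the second dose of the weekly study drug is administered". Subjects then attend on Day 10 and receive injections "in an outpatient fashion to ensure compliance on Days 15, 22, 29, 36, 43, 50, 57, 64 and 71". They are next in-house from Day 77.

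Section 5.1.1 lists injection site reactions among the primary endpoints, and they are the only local tolerability endpoint in Table 12-1.

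**The concern.** The look after the dosing day depends on there being an in-house day or a non-dosing outpatient visit before the next injection. In the middle of treatment there is neither. A site injected on Day 15, for example, is examined that day, 30 minutes or more after injection. The protocol then attaches no further inspection to it. The Day 22 assessment is timed from the Day 22 injection, and a pre-dose look is specified only for Day 1.

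This endpoint is built on examination. A Draize-type score, a diameter and a photograph can come only from a site that staff look at. Erythema or induration that appears later in the week, or lasts into the next, has no assigned moment at which to be scored. Duration is also affected. One escalation-stopping criterion in section 6.4.2 counts related moderate adverse events that last more than 7 days. Without a required look at the earlier site, the length of a local reaction is poorly documented.

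**Working it through.** The protocol gives no figure on this point, so the check is a count by day.

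**Inputs**
- Dosing days (sections 6.1 and 6.2): dose *k* falls on Day 1 + 7(*k* − 1), for *k* = 1 to 12, which gives Days 1, 8, 15, 22, 29, 36, 43, 50, 57, 64, 71 and 78.
- Outpatient visits during treatment (section 6.2): Days 10, 15, 22, 29, 36, 43, 50, 57, 64 and 71, ten in all. Nine are dosing days, so 10 − 9 = 1 is not: Day 10.
- In-house days: to Day 8, then Day 77 to Day 82 (Day 81 for some subjects).
- After the last dose: Day 85, the final inspection.

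**Rule applied.** A dose has a later required look if an in-house day or a non-dosing outpatient visit falls after its injection and before the next dose. For dose 12 the limit is Day 85.

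| Dose | Day | Required looks after the day of injection | Next listed visit |
|---|---|---|---|
| 1 | 1 | Days 2 to 7 | Day 2 |
| 2 | 8 | Day 10 | Day 10, 2 days later |
| 3 to 10 | 15, 22, 29, 36, 43, 50, 57, 64 | none | 7 days later, itself a dosing day |
| 11 | 71 | Day 77 | Day 77, 6 days later |
| 12 | 78 | Days 79 to 81 (or 82) and 85 | Day 79 |

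**Result.** Doses with a later look: 1, 2, 11 and 12, so 4 of 12. Doses without: 12 − 4 = 8, and 8/12 = 67%. The count is the same whether the second in-house period ends on Day 81 or Day 82. The week 8 MRI may bring a subject in separately before Day 57, but no injection-site inspection is attached to it.

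**Do the Appendix A footnotes change this?** Their wording differs between tables.
- Table 16-1: the footnote covers Day 1 only.
- Table 16-2: the rule for later doses repeats section 9.1.21, but is attached to the footnote on inflammatory biomarkers.
- Tables 16-3 to 16-5: the reference to non-dosing days comes later in the sentence, so the clause could be read as covering every outpatient visit. On that reading the next look for dose 3 is Day 22 − Day 15 = 7 days after injection, and the same holds through dose 10 (71 − 64 = 7). It still does not say that the earlier site is the one examined.

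**The case against.** The day count is not in dispute. The case against concerns what follows from it.

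- **Reactions are still asked about.** A reader might infer that delayed reactions in weeks 3 to 10 are missed unless the subject volunteers them. Section 10.4.1 does not support that. It requires the Investigator to assess subjective adverse events at outpatient visits, and its example question covers the time since the last visit. Itching and pain can be reported this way. This stands. What remains is lower sensitivity for mild visible signs, and no score for a reaction that has gone.
- **Staff may see the old site anyway.** Sites are marked, all injections go into the abdominal wall, and section 9.1.21 speaks of injections in the plural. A reaction still visible at 7 days may well be noticed. This is fair, but it describes what could happen rather than what is required.
- **The antibody samples.** A reader might infer that the gap coincides with immune-mediated reactions, because samples are taken "post first dosing on Day 22, 50, 78, 85 and 99". These are sampling days, not known times of onset. Two of them, Days 78 and 85, fall in the stretch with inspection after dose 12. The protocol reports no adverse injection-site findings in animals, and no drug-related dermatologic events so far in the single-dose study (section 4.3). The timing argument should not be made.
- **Comparison between arms.** The schedule is the same for active and placebo, subjects and clinical staff are blinded, the analysis is descriptive, and no stopping rule is specific to the injection site. This stands, so the schedule gives no reason to expect collection to differ by arm. The recorded incidence and duration can still be too low in absolute terms.

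**Conclusion.** The point holds as a gap in required assessment. For 8 of 12 doses (67%) the protocol requires inspection only on the day of injection, and no passage requires the earlier site to be re-examined. Delayed or persistent reactions to these doses may be under-recorded in incidence, severity score and duration.

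It would go too far to say that incidence is certain to be understated, or that it reflects mainly doses 1, 2, 11 and 12. Every dose has a dosing-day look, adverse events are sought at each visit, and the documents give no rate of delayed local reactions from which to size a loss.

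The count assumes that daily in-house looks include the most recent injection site, so that Day 77 serves dose 11. It also takes section 9.1.21 as the governing rule where the footnotes differ. The change is worth making because this is a primary endpoint that depends on examination and the visits already exist.

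**What to change.** In section 9.1.21 and the injection-site footnotes of Tables 16-1 to 16-5, use one common wording: at each weekly dosing visit, before dosing, inspect and score the previous week's marked site, and ask the subject specifically about reactions there since the last visit. Then assess the new site 30 minutes or more after injection, as now planned. Move the Table 16-2 text to the injection-site footnote.

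The cost is protocol and eCRF wording and about a minute per existing visit, with no new visit or staff.

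Limits and downsides:
- Reactions that appear and resolve within the week will be captured by report only, without a score.
- Slightly more mild reactions will be recorded.
- The specific question departs from the non-specific enquiry of section 10.4.1. Record its answers as part of the local tolerability assessment so that they can be told apart from unprompted reports.
- If the change applies only to cohorts still to start, collection will differ between cohorts while placebo is pooled across them (section 12.2.5). The summaries should then show which cohorts followed which rule.
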